4.1.1. Part A: Single Ascending Doses in Healthy Participants

Approximately 35 healthy adult participants will be enrolled at 1 or more sites into the proposed cohorts listed below. Participants may only participate in 1 cohort.

Participants in the single dose cohorts will be randomized sequentially as follows:

- Cohort 1 (n=4): PF-07261271 mg (n=2) or placebo (n=2), IV;
- Cohort 2 (n= 4): PF-07261271 mg (n=2) or placebo (n=2), IV;
- Cohort 3 (n=6): PF-07261271 mg (n=4) or placebo (n=2), IV;
- Cohort 4 (n=8): PF-07261271 mg (n=6) or placebo (n=2), IV.

An optional dose cohort may be added based on emerging PK and safety/tolerability data. This cohort (Cohort 7) will be randomized as follows:

Cohort 7 (n=8): single PF-07261271 dose (n=6) or placebo (n=2), IV.

An optional cohort of Japanese participants may be included in the study at the discretion of the sponsor. This cohort (Cohort 8) will be randomized as follows:

Cohort 8 (n=5): PF-07261271 at dose tested in the sequence above that is determined
to be safe and well-tolerated based on emerging data from preceding cohorts (n=4) or
placebo (n=1), IV or SC.

Within approximately 35 days of successful completion of the screening process, eligible participants will be randomized to receive a single IV infusion of PF-07261271 or placebo. In order to mitigate any unanticipated acute safety risks within the SAD cohorts, sentinel dosing will be implemented in all SAD cohorts (ie, cohorts where the dose being tested is the highest administered in the study to date). For sentinel dosing, the first 2 participants (1 active:1 placebo) will be dosed and monitored for at least 24 hours to assess safety and tolerability prior to dosing the remaining participants in the cohort. If the dose level for the first 2 sentinel participants is determined to have an acceptable safety and tolerability profile, as judged by the investigator, the remaining participants within the cohort will be dosed.

Single dose cohorts will be enrolled sequentially in a dose escalating fashion starting from the lowest proposed dose (mg).

For Cohorts 1-2, if a single participant dosed with active drug meets 1 of the dose escalation stopping criteria mentioned in Section 6.6.1, based on a discussion between sponsor and investigators, 4 more participants may be added to the cohort (2 active:2 placebo). If a cohort is extended with 4 additional participants as described above, dose escalation stopping decisions (Section 6.6.1) will be based on the data from all 4 participants receiving active study intervention.

During Part A (SAD) of the study, escalation to subsequent dose levels will occur following the sponsor and investigator's review of available safety and PK data through study Day 15 for the immediately previous cohort (and emerging clinical and PK data from all enrolled cohorts). Dosing in this part may be adjusted depending upon the actual exposure of PF-07261271 observed in humans at lower doses. If, based on the observed data, the subsequent dose projected group mean C_{max} or (data permitting) are higher than the PK exposure limit in humans of pg/mL or (data permitting) are higher than the µg•hr/mL, respectively (determined as 1/10th of the mean exposures observed at NOAEL in the 3-month cynomolgus monkey toxicity study) that dose will not be explored.

Participants will be admitted into the CRU approximately 1 day prior to dosing and may be required to stay overnight in the study center through completion of Day 5 evaluations as per the SoA. Participants may be discharged after Day 3 procedures have been completed and before Day 5, at the investigator's discretion to accommodate participant scheduling and if considered safe to do so. In this case, Day 5 activities will be conducted as an outpatient. Day 4 activities will be performed only if participants are not discharged after Day 3 procedures. For Cohorts 1-4, 7 and 8, the final follow-up visit will be determined based on safety and PK data emerging from previous cohort(s), which may be earlier than Day 451 (±7 days). The final follow-up visit will be based on at least 1 of the following criteria:

- approximately ≥5 times the observed half-life, OR
- of sufficient duration to have projected exposures decrease below ADA drug tolerance levels, OR
- to a level of exposure at which clinically significant pharmacologic effects on immune function is unlikely (eg, <IC₈₀).

Based on emerging data from previous and ongoing single dose cohorts, doses planned may be modified and other doses may be explored in additional cohorts. If the exposures in the subsequent dose is projected to exceed the exposure limits pre-specified, that dose will not be explored.

4.1.2. Part B: Multiple Doses in Healthy Participants

One multiple SC dose cohort of PF-07261271 (mg) and 1 optional multiple dose cohort in healthy participants are planned. Participants in the multiple dose cohorts, will be randomized as follows:

- Cohort 5 (n=8): PF-07261271 mg (n=6) or placebo (n=2), SC
- Optional Cohort 6 (n=8): Multiple dose active (n=6) or placebo (n=2), IV or SC.

Initiation of the first multiple dose (Cohort 5) will occur following the sponsor and investigator's review of available safety and PK from a SAD dose level that provides higher exposures than projected for Cohort 5 after repeat doses in addition to the accumulated safety from the previous SAD cohorts. The starting dose of mg for the initial multiple dose cohort may be adjusted, based on emerging safety and PK data from the single dose cohorts. Progression to the next multiple dose may proceed after review of:

- Safety/tolerability data through Day 15 and PK data through Day 8 of the single dose that is no lower than the planned SC dose in next MD cohort;
- Cumulative safety and PK data from the previous single dose cohorts;
- Safety/tolerability and PK data through Day 36 (8 days following the second dose) of the ongoing MD cohort.

If, based on the observed data, projected group mean C_{max} or at the subsequent MD dose level is μ g/mL or μ g/mL respectively following the second dose, that dose will not be explored.

An optional second MD cohort may be enrolled for further investigation of multiple doses as needed in light of emerging safety and PK data. The dose, frequency, and route of administration (IV or SC) for this cohort will be determined following a review of the cumulative safety and PK data from the single dose cohorts and at least through of the mg MD cohort.

Participants will be confined to the CRU starting on the day prior to dosing and through at least

Participants may remain confined in CRU longer at the discretion of the investigator. Participants will return for outpatient visits per the SoA, with the final follow-up visit to be determined based on safety and PK data emerging from previous SAD and MD cohort(s), which may be earlier or later than Day 471 (±7 days). The final follow-up visits will be based on at least 1 of the following criteria:

- approximately ≥5 times the observed half-life, OR.
- of sufficient duration to have projected exposures decrease below ADA drug tolerance levels, OR

 to a level of exposure at which clinically significant pharmacologic effects on immune function is unlikely (eg, <IC₈₀).

Based on emerging PK data, additional samples may be added to ensure PK is adequately characterized. Based on emerging data from previous and ongoing single and multiple dose cohorts, doses planned may be modified and other doses and/or dosing regimens (eg, Q4W) may be explored in separate cohorts. If the exposures in the subsequent dose are projected to exceed the pre-specified exposure limits, after repeat doses, that dose will not be explored.

4.2. Scientific Rationale for Study Design

Study C4631001 represents the first time PF-07261271 will be administered to humans and hence will employ an escalating dose design initially using single doses and then, once the safety and tolerability of higher single doses has been demonstrated, repeat doses.

Part A (SAD phase) of Study C4631001 will be initiated with a starting dose of estimated to have sufficient safety margin (see Justification for Dose, Section 4.3) with dose escalation continuing up to the maximum planned dose as long as projected exposures do not meet any stopping criteria. Part B (MD phase) of the study will be initiated once adequate safety data are available from a higher dose in the SAD phase of the study (see Section 4.1.2). An optional MD cohort is planned to study additional dose levels in case of lower than projected bioavailability and accumulation or SC related safety signals. Study C4631001 uses a placebo-controlled, blinded design to minimize bias which is justified in this early clinical study to provide a reference for safety and tolerability.

The study will be conducted in healthy participants (as defined by the inclusion/exclusion criteria) in order to establish the safety, tolerability, and PK profile of PF-07261271 prior to exposure in patient populations. Although healthy participants can derive no potential benefit from exposure to PF-07261271, there is extensive experience with inhibitors of the cytokines targeted by PF-07261271 that suggests that PF-07261271 will be well-tolerated and have an acceptable safety profile in healthy participants.

PF-07261271 is designed to inhibit sTL1A, IL-12, and IL-23 cytokines, and is expected to bind these cytokines at the site of action. To understand target engagement, total levels of if feasible will be measured.

Both adult male and female participants (including WOCBP) are eligible for enrollment into the study. Since human reproductive safety data are not available for PF-07261271, female participants must either be confirmed to be of non-childbearing potential or, if of childbearing potential, to be using at least 1 form of highly effective method of contraception as detailed in Appendix 4. As an additional safety measure, WOCBP will be required to have a negative pregnancy test prior to randomization and at pre-specified visits per the SoA (including before each repeat dose in the MD cohorts), and contraception checks will be performed at all outpatient visits.

No barrier method of contraception (eg, condom) is warranted for male participants as the potential exposure to PF-07261271 via semen to partners of male participants is anticipated

to be very low. The calculated safety margin between the estimated maternal exposure due to seminal transfer at maximum dose/exposure proposed in human and the MABEL of PF-07261271 is in excess of 10,000-fold. Additionally, PF-07261271 does not have genotoxicity concerns.

Healthy Japanese participants may be enrolled in a separate, optional cohort to provide a preliminary characterization of the safety, tolerability, PK, and PD profile of PF-07261271, to support potential inclusion of Japanese patients in future studies.

Risks to study participants will be minimized by cautious dose escalation in an inpatient setting, with careful assessment and ongoing review of emerging safety data. Additionally, sentinel dosing will be implemented in all SAD cohorts (ie, cohorts where the dose being tested is the highest administered dose in the study to date). Together, the implementation of sentinel dosing in SAD cohorts and the dose escalation rules (Section 6.6.1) are expected to minimize risk to study participants while providing key safety and tolerability information.

Since all mAbs have a potential for immunogenicity, all participants will be monitored closely for signs and symptoms of immunogenicity, including infusion reactions and anaphylaxis. Blood samples will be collected for measurement of ADA in all participants. Samples determined to be positive for ADA may be further characterized for NAbs. If emerging data suggests ADA and/or NAb levels are still significantly associated with any safety concerns present at the last scheduled visits in MD cohorts, additional follow-up visit(s) with ADA/NAb assessment may be required in the next cohorts.

Since this molecule is designed to reduce inflammation, there is a potential risk of infection due to immune suppression. All participants will be screened and excluded if they have active or latent infections, and monitored for evidence of infection with laboratory testing and AE surveillance.

Participants who discontinue prior to completion of the study for other than safety reasons may be replaced, at the discretion of the investigator and sponsor.

For all other cohorts in Parts A and B, the final follow-up visit will be determined based on safety and PK data emerging from previous cohort(s) based on one of the criteria detailed in Sections 4.1.1 and 4.1.2.

4.2.1. Choice of Contraception/Barrier Requirements

Studies to evaluate the developmental toxicity of PF-07261271 have not been conducted. Therefore, the use of a highly effective method of contraception for WOCBP is required (see Appendix 4).

4.2.2. Collection of Retained Research Samples

Retained Research Samples will be collected and stored for further analyses which may, for example, provide greater understanding of the study intervention.

4.3. Justification for Dose

Doses presented are projected based on nonclinical data and may be modified based on emerging safety, tolerability, and PK data.

4.3.1. Prediction of Human PK

PF-07261271 has been engineered for extended half-life in a manner similar to PF-06817024 (ClinicalTrials.gov Identifier: NCT02743871), an anti-IL-33 mAb that has already been studied in humans, and it is expected to have similar PK properties. PK simulations for PF-07261271 assume a 2-compartment PK with the following parameters:

[figure not shown]
Based on these

parameters, the half-life is projected to be approximately days.

4.4. End of Study Definition

The end of the study is defined as the date of the last visit of the last participant in the study.

A participant is considered to have completed the study if they have completed all periods of the study, including the last visit as shown in the SoA.

5. STUDY POPULATION

This study can fulfill its objectives only if appropriate participants are enrolled, including participants across diverse and representative racial and ethnic backgrounds. Use of a prescreening tool is utilized for study recruitment purposes, it will include collection of information that reflects the enrollment of a diverse participant population including, where permitted under local regulations, age, sex, and race, and ethnicity. The following eligibility criteria are designed to select participants for whom participation in the study is considered appropriate. All relevant medical and nonmedical conditions should be taken into consideration when deciding whether a particular participant is suitable for this protocol.

Prospective approval of protocol deviations to recruitment and enrollment criteria, also known as protocol waivers or exemptions, is not permitted.

5.1. Inclusion Criteria

Participants are eligible to be included in the study only if all of the following criteria apply:

Age and Sex:

 Participants aged 18 to 65 years (or the minimum age of consent in accordance with local regulations) at screening.

Refer to Appendix 4 for reproductive criteria for male (Section 10.4.1) and female (Section 10.4.2) participants.

Male and female participants who are overtly healthy as determined by medical evaluation including medical history, physical examination, vital sign assessments, laboratory tests, and 12-lead ECGs.

Other Inclusion Criteria:

- BMI of 17.5 to 30.5 kg/m²; and a total body weight >50 kg (110 lb).
- Capable of giving signed informed consent as described in Appendix 1, which
 includes compliance with the requirements and restrictions listed in the ICD and in
 this protocol.

Additional criterion for optional Japanese cohort only:

Participants who have four Japanese biological grandparents born in Japan.

5.2. Exclusion Criteria

Participants are excluded from the study if any of the following criteria apply:

Medical Conditions:

- Evidence or history of clinically significant hematological, renal, endocrine, pulmonary, gastrointestinal, cardiovascular, hepatic, psychiatric, neurological, or allergic disease (including drug allergies, but excluding untreated, asymptomatic, seasonal allergies at the time of dosing).
 - History of HIV infection; infection with hepatitis B, or hepatitis C viruses according to protocol-specific testing algorithm.
 - For hepatitis B, participants will undergo testing for HBsAg and HBcAb. Participants who are HBsAg positive will not be eligible for this study. Participants who are HBsAg negative but HBcAb positive will be reflex tested for HBsAb. Please refer to Appendix 2 for testing algorithm and reflex testing.
 - For hepatitis C, all participants will undergo testing for HCVAb during screening. Participants who are HCVAb positive will be reflex-tested for HCV RNA. Participants who are HCVAb and HCV RNA positive are not eligible for the study.
 - Evidence of active, latent, or inadequately treated infection with Mycobacterium TB.
 - If a participant previously received an adequate course of therapy for either latent (9 months of isoniazid in a locale where rates of primary multidrug resistant TB infections are <5% or an acceptable alternative regimen) or active (acceptable multi-drug regimen) TB infection, TB tests

do not need to be obtained. Details of previous course of therapy (eg, medication(s) used, dose, duration of therapy) should be documented in the source documentation.

- Any malignancies or history of malignancies with the exception of adequately treated or excised non-metastic basal cell or squamous cell cancer of the skin, or cervical carcinoma in situ.
- History of any lymphoproliferative disorder such as EBV related lymphoproliferative disorder, history of lymphoma, leukemia, or signs and symptoms suggestive of current lymphatic or lymphoid tissue disease.
- Other medical or psychiatric condition including recent (within the past year) or
 active suicidal ideation/behavior or laboratory abnormality or other conditions or
 situations related to COVID-19 pandemic that may increase the risk of study
 participation or, in the investigator's judgment, make the participant inappropriate for
 the study.
 - History of febrile illness within 5 days prior to the first dose of investigational product.
 - Significant trauma or major surgery within 1 month of the first dose of study drug.

Prior/Concomitant Therapy:

- 3. Recent exposure to live or attenuated vaccines within 28 days of the screening visit.
- 4. Use of prescription or nonprescription drugs and dietary and herbal supplements within 7 days or 5 half-lives (whichever is longer) prior to the first dose of study intervention. (Refer to Section 6.9 Prior and Concomitant Therapy for additional details).
- Current use of any prohibited concomitant medication(s). Refer to Section 6.9 Prior and Concomitant Therapy.

Prior/Concurrent Clinical Study Experience:

6. Previous administration with an investigational product (drug or vaccine) within 30 days (or as determined by the local requirement) or 5 halflives preceding the first dose of study intervention used in this study (whichever is longer).

Diagnostic Assessments:

7. Screening supine BP ≥140 mm Hg (systolic) or ≥90 mm Hg (diastolic), following at least 5 minutes of supine rest. If BP is ≥140 mm Hg (systolic) or ≥90 mm Hg

- (diastolic), the BP should be repeated 2 more times and the average of the 3 BP values should be used to determine the participant's eligibility.
- 8. Standard 12-lead ECG that demonstrates clinically relevant abnormalities that may affect participant safety or interpretation of study results (eg, QTcF >450 ms, complete LBBB, signs of an acute or indeterminate- age myocardial infarction, ST-T interval changes suggestive of myocardial ischemia, second- or third- degree AV block, or serious bradyarrhythmias or tachyarrhythmias). If the uncorrected QT interval is >450 ms, this interval should be rate-corrected using the Fridericia method only and the resulting QTcF should be used for decision making and reporting. If QTcF exceeds 450 ms, or QRS exceeds 120 ms, the ECG should be repeated twice and the average of the 3 QTcF or QRS values used to determine the participant's eligibility. Computer-interpreted ECGs should be overread by a physician experienced in reading ECGs before excluding a participant.
- Participants with ANY of the following abnormalities in clinical laboratory tests at screening, as assessed by the study-specific laboratory and confirmed by a single repeat test, if deemed necessary:
 - AST or ALT level ≥1.5 × ULN;
 - Total bilirubin level ≥1.5 × ULN; participants with a history of Gilbert's syndrome may have direct bilirubin measured and would be eligible for this study provided the direct bilirubin level is ≤ ULN.

Other Exclusion Criteria:

- 10. History of drug or alcohol abuse or binge drinking and/or any other illicit drug use or dependence within 6 months of Screening. Binge drinking is defined as a pattern of 5 (male) and 4 (female) or more alcoholic drinks in about 2 hours. As a general rule, alcohol intake should not exceed 14 units per week (1 unit = 8 ounces (240 mL) beer, 1 ounce (30 mL) of 40% spirit, or 3 ounces (90 mL) of wine).
 - A positive urine drug test. A positive test for cannabinoid-based compounds (eg, THC, CBD, etc) will not be considered exclusionary.
 - Participants with >20 cigarettes a day intake or more than 30 pack years.
- Blood donation (excluding plasma donations) of approximately 1 pint (500 mL) or more within 30 days prior to screening.
- History of sensitivity to heparin or heparin-induced thrombocytopenia.
- Unwilling or unable to comply with the criteria in the Lifestyle Considerations section of this protocol.

14. Investigator site staff directly involved in the conduct of the study and their family members, site staff otherwise supervised by the investigator, and sponsor and sponsor delegate employees directly involved in the conduct of the study and their family members.

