6.9.2. Prohibited During the Study

Participants are required to discontinue and avoid using certain medications and treatments. Participants should be instructed at each visit to contact the study site investigator promptly if there are any intended changes or additions to concomitant medications. Prohibited medications during the study include:

- Oral and parenteral corticosteroids within 4 weeks prior to the first dose of study intervention.
- Current or anticipated use of protein therapeutics including but not limited to
 targeted therapies within 6 months of the
 first dose of study intervention.
- Herbal medications with presumed anti-inflammatory properties, or that are known to have an effect on drug metabolism (eg, St. John's Wort) must be discontinued at least 7 days or 5 half-lives (whichever is longer) before the first dose of study intervention.
- Oral and parenteral anti-infectives within 2 weeks or 5 half-lives (whichever is longer) before the first dose of study intervention.
- Herbal and prescription medications for treatment of chronic diseases including but not limited to hematological, renal, endocrine, pulmonary, gastrointestinal, cardiovascular, hepatic, psychiatric, neurological, or allergic disease.
- Any other investigational drug(s) within 4 weeks of the first dose of study intervention or 5 half-lives (whichever is longer), or at any time during the study.

A protocol deviation is to be completed for any participant that takes a prohibited treatment or medication during the study and the sponsor is to be notified.

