8. STUDY ASSESSMENTS AND PROCEDURES

8.1. Administrative Procedures

The investigator (or an appropriate delegate at the investigator site) must obtain a signed and dated ICD before performing any study-specific procedures.

Study procedures and their timing are summarized in the SoA. Protocol waivers or exemptions are not allowed.

Adherence to the study design requirements, including those specified in the SoA, is essential and required for study conduct.

All screening evaluations must be completed and reviewed to confirm that potential participants meet all eligibility criteria. The investigator will maintain a screening log to record details of all participants screened and to confirm eligibility or record reasons for screening failure, as applicable.

Participants will be screened within 35 days prior to administration of the study intervention to confirm that they meet the study population criteria for the study. If the time between screening and dosing exceeds 35 days as a result of unexpected delays (eg, delayed drug shipment), then participants do not require recollection of banked biospecimens.

A participant who qualified for this protocol but did not enroll from an earlier cohort/group may be used in a subsequent cohort/group without rescreening, provided laboratory results obtained prior to the first dose administration meet eligibility criteria for this study. In addition, other clinical assessments or specimen collections, eg, retained research samples, may be used without repeat collection, as appropriate.

Every effort should be made to ensure that protocol-required tests and procedures are completed as described. However, it is anticipated that from time to time there may be circumstances outside the control of the investigator that make it unfeasible to perform the test. In these cases, the investigator must take all steps necessary to ensure the safety and well-being of the participant. When a protocol-required test cannot be performed, the investigator will document the reason for the missed test and any corrective and preventive actions that they have taken to ensure that required processes are adhered to as soon as possible. The study team must be informed of these incidents in a timely manner.

Safety/laboratory/analyte results that have been collected for the purposes of this study and could unblind the study will not be reported to investigative sites or other blinded personnel until the study has been unblinded.

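### Exclusion 3 counts its 28-day live-vaccine window from screening, not first dose, so whether a vaccination between the two is caught depends on the site's reading and the screening date

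*Protocol*

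**What the plan says.** Protocol Section 5.2, Exclusion 3, excludes "Recent exposure to live or attenuated vaccines within 28 days of the screening visit". The synopsis carries the same sentence, so the anchor is not a slip in one place.

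The screening visit is not a fixed distance from dosing. Section 8.1 states: "Participants will be screened within 35 days prior to administration of the study intervention". The screening column of the Schedule of Activities (SoA, Tables 1 and 3) spans Day -35 to Day -2. Section 8.1 also says that a participant who qualified earlier but did not enroll "may be used in a subsequent cohort/group without rescreening". The condition attached to this concerns laboratory results, and no maximum interval is given.

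The neighbouring criteria use a different anchor:
- Exclusion 4 (drugs and supplements) applies "within 7 days or 5 half-lives (whichever is longer) prior to the first dose of study" intervention.
- Exclusion 6 ("Previous administration with an investigational product (drug or vaccine) within" 30 days) ends with "or 5 halflives preceding the first dose of study intervention used in this study".
- The febrile-illness (5 days) and trauma or major surgery (1 month) items under Exclusion 2 also refer to first dose.

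On risk, Section 4.2 says that "there is a potential risk of infection due to immune suppression", and Section 2.3.1 lists serious infection as a potential risk. Section 6.9.2 opens its list with "Prohibited medications during the study include". Its six bullets show no vaccine entry, although one bullet, on protein therapeutics, is partly blacked out.

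**The concern.** What matters for a live vaccine given to someone about to receive an immune-modulating antibody is the time from vaccine to first exposure. A window counted from a movable visit does not control that time. On a look-back reading, the days left open are those nearest the dose, and the order of protection is reversed: with screening on Day -35, a vaccine on Day -60 excludes and a vaccine on Day -20 does not.

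At stake is the consistent application of an eligibility rule in healthy volunteers for whom no clinical benefit is expected, in a protocol that itself lists infection as a risk. No sample size, power or endpoint calculation depends on it.

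**Working it through.** The plan gives no figure to reproduce; this is calendar arithmetic on study days.

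**Inputs**
- Window length: 28 days, from screening (Section 5.2, Exclusion 3).
- Screening on Day -S, with S from 2 to 35 (SoA; Section 8.1). There is no Day 0, so Day -k is k days before the Day 1 dose.
- Exclusion 4: 7 days before first dose, if a vaccine counts as a drug. I assume its half-life clause adds nothing for a live vaccine.

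**Formulas.** Count the days after screening and before dosing that stay uncovered:
- Look-back reading: S − 1.
- Look-back plus Exclusion 4: max(0, S − 8).
- Two-sided reading (28 days either side of screening): max(0, S − 29).
- Two-sided plus Exclusion 4: max(0, S − 36).

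| Screening | Look-back | Look-back + Excl. 4 | Two-sided | Two-sided + Excl. 4 |
|---|---|---|---|---|
| Day -35 | 34 (Days -34 to -1) | 27 (Days -34 to -8) | 6 (Days -6 to -1) | 0 |
| Day -28 | 27 (Days -27 to -1) | 20 (Days -27 to -8) | 0 | 0 |
| Day -14 | 13 (Days -13 to -1) | 6 (Days -13 to -8) | 0 | 0 |
| Day -8 | 7 (Days -7 to -1) | 0 | 0 | 0 |
| Day -2 | 1 (Day -1) | 0 | 0 | 0 |

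**Reversed order.** With S = 35, the look-back window covers Days -63 to -35, because 35 + 28 = 63. Day -60 lies inside it and Day -20 outside. Day -20 is also outside the 7 days of Exclusion 4.

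**Carry-over.** Within the 35-day limit, the two-sided reading plus Exclusion 4 closes every day. For a participant carried to a later cohort, S has no stated limit. Once S exceeds 36, even that most favourable combination leaves days open: S = 37 gives 37 − 36 = 1 day, Day -8.

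**Effect of the anchor alone.** The same 28 days counted back from first dose cover Days -28 to -1 for every S. For S = 35, the days that the present rule excludes and this window would not are:
- on the look-back reading, Days -63 to -35 (63 − 35 + 1 = 29 days);
- on the two-sided reading, Days -63 to -29 (63 − 29 + 1 = 35 days).

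**The case against.** The strongest reply is that the large gap needs both the look-back reading and the earliest screening date. The criterion counts from the visit without saying before it, while Exclusions 4 and 6 and the blood-donation criterion do state a direction. A two-sided reading is therefore open, and with Exclusion 4 it leaves nothing uncovered inside the 35-day window. This stands as a limit on size. It does not settle the meaning: the criterion speaks of recent exposure, and the substance-use criterion uses a similar phrase about screening for what is plainly history. Exclusion 6 names drugs and vaccines separately, so Exclusion 4 is not a clear safeguard for vaccines.

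There are also partial controls. Section 6.9.1 has treatments in the 35 days before first dose recorded. The SoA repeats the eligibility and medication review on Day -1. Exclusion 2 allows investigator judgment and bars recent febrile illness. These make an unnoticed vaccination less likely, but none is specific to vaccines, and the Day -1 review applies the same screening-anchored sentence.

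A reader might infer that nothing restrains vaccination after dosing. That is too strong. Section 6.9.1 asks that medication added in the first 3 months be confined to what is medically needed, Section 6.9.2 has participants report intended changes, and its list is not worded as exhaustive. Nor does infection risk rest on screening alone: Sections 2.3.1 and 4.2 also rely on laboratory monitoring and adverse-event surveillance.

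**Conclusion.** The point holds as a fault of wording in an eligibility criterion. With screening on Day -35, the uncovered interval is 34 days on the look-back reading, 27 if Exclusion 4 includes vaccines, 6 on a two-sided reading, and none on a two-sided reading with Exclusion 4. Later screening shrinks every figure; carry-over can enlarge them. The conclusion rests on the 28-day length as the sponsor set it. The documents give no basis for judging that length.

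Three stronger readings are not supported:
- **Contaminated safety or biomarker endpoints.** SAP Section 3.1.1 does not count events that began before first dose as treatment-emergent. C-reactive protein is not among the tests in Protocol Table 12. The biomarker analytes are blacked out, so nothing shows that a vaccine would shift them. A reaction starting after dosing could be counted, but the documents give no means of sizing that.
- **An unlimited vaccine-to-dose interval under carry-over.** What Section 8.1 leaves without a limit is the screening-to-dose interval. A long vaccine-to-dose interval is not the hazard.
- **A particular rule for live vaccines after dosing.** The documents state none, and this review proposes none.

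**What to change.** Reconcile the anchor of Exclusion 3, in Section 5.2 and the synopsis, with Exclusions 4 and 6, so that the sponsor's own 28-day window is stated relative to first dose and takes in vaccination after screening. Apply it at the Day -1 eligibility review already in the SoA; this also deals with carried-over participants.

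The sponsor should choose between two forms:
- **Replace** the screening anchor. Days -28 to -1 are covered whatever the screening date, but for Day -35 screening some people now excluded become eligible: Days -63 to -29 on the two-sided reading, Days -63 to -35 on the look-back reading. A vaccine on Days -34 to -29 falls after such a screening visit but outside the 28 days.
- **Extend** the present window forward to first dose. For Day -35 screening this covers Days -63 to -1 and admits nobody now excluded.

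Separately, the sponsor should reconcile Section 6.9.2 with the infection-risk statements in Sections 2.3.1 and 4.2 by stating its position on live vaccines after first dose.

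The cost is amendment wording and one question on Day -1, with an occasional participant vaccinated after screening being deferred. The Amendment 2 summary of changes already refers to an active multiple-dose cohort, so the change would reach only participants not yet dosed, probably those in later or optional cohorts.
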